Suicidality, mania/hypomania (exclusion-referral)	Beck Depression Scale (BDI)(Beck, Ward, Mendelson, Mock, & Erbaugh, 1961), MINI suicidality, (hypo) mania modules (D V Sheehan, 1998), Mood Disorder Questionnaire (Hirschfeld R, 2000), ASK Suicide-Screening Questionnaire (ASQ)(Horowitz, L.M., 2020)
Depression symptoms	Beck Depression Scale (BDI)(Beck, Ward, Mendelson, Mock, & Erbaugh, 1961), Patient Health Questionnaire-2 (PHQ-2) (Kroenke K, 2003)
Emotional reactivity	Self-Assessment Manikin (SAM) (Bradley MM, 1994)
Domestic violence	Revised conflict tactics scale (CTS2) (STRAUS, HAMBY, BONEY-MCCOY, & SUGARMAN, 1996)
Trauma history	Trauma History Screen (THS)(Carlson et al., 2011)
PTSD symptoms	Posttraumatic Stress Checklist (PCL-5)
Detailed alcohol use (exclusion-referral)	Alcohol Use Disorders Identification Test (AUDIT)(Babor, Higgins-Biddle, Saunders, Monteiro, & World Health Organization, 2001)
Drug use (exclusion-referral)	Drug Abuse Screening Test (DAST-10)(Skinner, 1982)
Social Support	Multi-dimensional Scale of Perceived Social Support (MSPSS) (Zimet GD, 1988)
Health-related disability	World Health Organization Disability Assessment Schedule (WHODAS)(Üstün et al., 2010)
Wellbeing and functioning changes due to COVID-19 pandemic	The Pandemic Emotional Impact Scale (Palsson O, et al., 2020)
Depression And Primary care Partnership for Effectiveness-implementation Research (DAPPER); Diabetes Mellitus (DM); Human Immunodeficiency Virus (HIV); Hypertension (HTN); Kenyan Shillings (KSH) (100KSH~1USD); Major Depressive	

Disorder (MDD); Mini International Neuropsychiatric Interview version 5.0 (MINI v. 5.0). * Accessibility measures; **Affordability measures.

Non-specialist training and treatment refinements for context

● **IPT:** Based on our experience training local community members to deliver IPT in the proposed region of research and other LMICs,(Jiang et al., 2014; [name] et al., n.d.; Onu et al., 2016; Zunner et al., 2015) we have developed a process of combining training in IPT with cultural adaptations, as needed, from IPT trainees.

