Acceptability and Appropriateness. Interview material will be recorded in audio files, transcribed and translated. Dedoose software will be used to analyze the resulting text using grounded theory. Grounded theory sorts data in three ways: through concepts, categories and propositions. Concepts are identified by seeking conceptual similarities among focus groups/interviews. These concepts are grouped to develop categories of concepts. Categories are then compared and grouped to develop propositions or theoretical constructs about the phenomena of interest. Dedoose software facilitates coding of observations to work toward the theoretical construct. Data will be collected using a “triangulation” technique that compares information from various sources (focus groups, individual interviews) in order to increase the reliability and validity of the findings. ***Feasibility and Fidelity.*** Feasibility and fidelity measures will be assessed by sample means and proportions, with 95% confidence intervals, and compared to pre-specified benchmarks (above).

Service delivery mechanism: availability and affordability. *Hypothesis 1c* will be addressed by calculating RE-AIM for IPT and fluoxetine according to the procedures outlined in Glasgow et al.(Glasgow, Vogt, & Boles, 1999) Then, we will then evaluate how RE-AIM scores correlate with availability and affordability measures (Table 2) for IPT versus fluoxetine. Finally, we will evaluate for mediation by treatment completion. Specifically, we will begin with logistical regression models of RE-AIM score including availability factors and affordability factors. If any significant relationships exist, we will construct figures of hypothetical relationships between variables that are significantly associated with RE-AIM score and create path diagrams, using effect sizes to identify potential causal pathways between availability, affordability and RE-AIM scores for IPT versus fluoxetine.

Table 2: Calculating RE-AIM from an Effectiveness-Implementation Hybrid Type I (SMART-DAPPER)(Farris, Will, Khavjou, & Finkelstein, 2007; Glasgow, Klesges, Dzewaltowski, Estabrooks, & Vogt, 2006)

1	Reach will be calculated as the ratio of study participants who are eligible for SMART-DAPPER compared with those who choose to participate. Reach is the first assessment of RE-AIM.
Effectiveness Outcomes	
2a	MDD and/or PTSD remission from IPT or fluoxetine at month 3 (IPT) and month 6 (fluoxetine).

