As it pertains to antidepressants and psychotherapy, the evidence base comparing “switching” versus “combining” treatment for non-remitters (second line treatment) is still developing. However, the field does have meta-analytic data on the differences between treating depression with antidepressants or psychotherapy alone, versus their combination. A 2009 meta-analysis (n=2036) which compared combination treatment (psychotherapy and pharmacotherapy) to pharmacotherapy alone for depression found an effect size of 0.31 (Cohen’s d).²⁷ A 2007 meta-analysis (n=903) found that the remission rate for major depression treated with psychotherapy and pharmacotherapy was better than psychotherapy alone, with an odds ratio of 1.5928, which when converted to a Cohen’s d is 0.25.²⁹ While specific studies have not yet been completed for IPT and PTSD, we leveraged the above-referenced meta-analyses of the effects of general psychotherapy and general pharmacotherapy to estimate sample size for the proposed study. Based on those studies, we would need approximately 164 per treatment arm to compare combined psychotherapy-medication treatment with medication alone, and 242 to compare combined psychotherapy-medication with psychotherapy, alone (using a two-sided alpha of 0.05 and power of 0.80). Using the conservative estimate, we will need 242 for each of the four treatment arms (968, total) after the second randomization (switch to fluoxetine, switch to IPT, combination after fluoxetine, combination after IPT). Note, this strategy uses fluoxetine treatment for 6 months as a first line treatment,

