consistent with the original R01 submission and responsive to reviewers' comments (summary statement response) on our funded U01 (DAPPER) study. While effectiveness data on treatment of depression in HICs (STAR*D) indicate that only approximately one-third remit with first line treatment, preliminary data from our current IPT study in Kisumu indicate remission rates over two-thirds. We will use a conservative estimate of the numbers entering the second randomization phase (non-remitters) and assume that half of study participants will need second-line treatment. Based on that estimate, the 968 participants randomized to the second stage of the SMART should represent 50% of those enrolled at the start of the trial, or 1936. Allowing for a 40% drop out rate across the 33 month duration of the study (domestic migration is common in Kenya³⁰), we will need 2710 participants for the SMART.

The additional number required for integration of the SMART design is 710 participants. Making a conservative assumption of ~20% prevalence of MDD and/or PTSD among primary care patients, we will screen 3,550 individuals to enroll 710 participants. While KCH and other Kisumu County Ministry of Health facilities see over 10,000 adult primary care patients per month, we will assume that only 20% of clinic attendees will undergo screening, and we will budget 3 months for recruitment. In order to avoid overwhelming mental health care providers, these 3 months of recruitment will be dispersed across a 18 month period: enrollment will halt when providers' caseloads are full and resume when at least 20% availability is regained. We will also work with Community Health Workers (CHWs) and Community Health Volunteers (CHVs) to

mobilize and sensitize the community about mental health services and refer community members to one of the health facilities for screening for the SMART-DAPPER study.

Eligibility criteria

Inclusion criteria:

- (1) KCH and other Kisumu County Ministry of Health facilities adult primary care outpatient clinic attendees who meet the threshold criteria for DSM-V for MDD and/or PTSD. .
- (3) Ability to attend weekly IPT sessions/fluoxetine monitoring in person or by telephone;
- (4) 18 years or older.

Exclusion criteria:

- (1) Cognitive dysfunction compromising ability to participate in IPT or accurately take fluoxetine (lack of orientation to person, place, time and situation);

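### The availability and affordability path analysis keeps only significant factors and names no IPT-versus-fluoxetine contrast, so weak retained effects tend to be exaggerated and apparent arm differences can be chance

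*Protocol*

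**What the plan says.** The analysis is in the Protocol under Service delivery mechanism: availability and affordability. After calculating RE-AIM for each treatment, the investigators will "evaluate how RE-AIM scores correlate with availability and affordability measures (Table 2) for IPT versus fluoxetine". They then turn to mediation by treatment completion, where "we will begin with logistical regression models of RE-AIM score including availability factors and affordability factors". The selection rule follows: "If any significant relationships exist, we will construct figures of hypothetical relationships between variables that are significantly associated with RE-AIM score". Path diagrams are built from those variables, "using effect sizes to identify potential causal pathways between availability, affordability and RE-AIM scores for IPT versus fluoxetine".

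The section gives no significance level, multiplicity rule, validation step, treatment term, factor-by-treatment interaction or test of a difference between paths. The SAP does not mention RE-AIM or path analysis. The only interaction it specifies is time by group, for the clinical outcomes.

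Two cross-references do not resolve. Hypothesis 1c, which this analysis is meant to address, is absent from the Hypothesis and Specific Aims list. Table 2, cited for the availability and affordability measures, lists RE-AIM components. The matching items are in Table 1, whose footnote stars two accessibility items (proximity, attendance challenge) and two affordability items (transport cost, opportunity cost).

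**The concern.** Two features of the rule cause trouble, and both are visible in the text.

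First, the data that decide which factors enter the diagram also supply the effect sizes on it. Estimates that pass a significance filter are biased away from zero, and the bias grows as power falls. A factor with a real but modest effect that misses significance vanishes from the picture, so the diagram understates what may act on uptake and outcome.

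Second, the stated output is a comparison of treatments, but no quantity is defined that compares them. A difference between arms needs an estimate of that difference with its own interval. Without one, a reader cannot tell a real difference in access barriers from sampling variation.

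The Protocol's Significance section promises policy makers a menu of options with implementation values. A barrier wrongly attributed to one treatment, or drawn too large, could misdirect scale-up effort.

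**Working it through.** The section states no alpha, sample size, power or effect size, so it has no figure to reproduce. The check asks how the stated rule behaves.

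**Inputs**
- Candidate factors: 4, the starred items of Table 1. This assumes that availability in this section means the accessibility items.
- Alpha: 0.05 two-sided. The Protocol gives this only for sample size ("using a two-sided alpha of 0.05 and power of 0.80"), so its use here is an assumption.
- Sample size: 2710 in total ("we will need 2710 participants for the SMART"). With the planned 40% dropout, 2710 × 0.6 = 1626 remain, or 813 per arm at 1:1.
- Outcome rate 50% and factors scaled to one SD. These are assumptions.

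**Step 1. Selecting a null factor.** For k independent tests the chance of at least one selection is 1 − 0.95^k.
- Pooled model, k = 4: 1 − 0.95^4 = 18.5%.
- Separate models in each arm, k = 8: 1 − 0.95^8 = 33.7%.
- Range for a pooled model with another count of tests: 9.8% at k = 2, 22.6% at k = 5, 33.7% at k = 8.

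**Step 2. Exaggeration of a retained effect.** Let μ be the true effect divided by its standard error. Ignoring the negligible far tail, the expected retained estimate divided by the truth is 1 + φ(μ − 1.96) / [μ Φ(μ − 1.96)].
- 50% power, μ = 1.96: 1 + 0.399 / (1.96 × 0.50) = 1.41.
- 80% power, μ = 2.80: 1 + 0.280 / (2.80 × 0.80) = 1.12.
- 95% power, μ = 3.60: 1.03.

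**Step 3. The same at this trial's size.** For a single factor, SE(log OR) ≈ 1/√(N × 0.25), which is 0.0496 at N = 1626 and 0.0384 at N = 2710.

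| True OR per SD | N = 1626: power, exaggeration | N = 2710: power, exaggeration |
|---|---|---|
| 1.05 | 16.6%, 2.53 | 24.6%, 2.01 |
| 1.10 | 48.5%, 1.43 | 69.9%, 1.20 |
| 1.15 | 80.5%, 1.12 | 95.3%, 1.03 |
| 1.20 | 95.7%, 1.03 | 99.7%, 1.00 |
| 1.30 | about 100%, 1.00 | about 100%, 1.00 |

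Fitting four factors together within one arm costs power. In a simulation with 813 per arm and factor correlation 0.3 (assumed; 1,500 runs per setting), exaggeration was 2.1 at OR 1.1, 1.27 at OR 1.2, 1.07 at OR 1.3 and 1.01 at OR 1.5.

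**Step 4. Testing interactions instead.** With no true arm difference, four unadjusted interaction tests give at least one false difference with probability 1 − 0.95^4 = 18.5%. The simulation gave 16–20%. At 0.05/4 = 0.0125 per test the figure is 1 − 0.9875^4 = 4.9%.

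**The case against.** The strongest reply is that this is a secondary implementation analysis, already worded with care. The relationships are called hypothetical and the pathways potential, and nothing here touches the primary result. At this sample size a factor of any practical strength is retained with almost no inflation. All of that stands, and it limits the size of the point. Careful wording does not remove selection bias from the numbers printed on a diagram, however, and causal pathways by treatment remain the stated output.

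A reader might infer that the plan will report treatment-specific pathways where none differ, by screening each arm and treating significance in one arm only as a difference. That procedure would perform badly. For a factor with the same effect in both arms and power p in each, the chance of significance in exactly one arm is 2p(1 − p): 42% at p = 0.3, 50% at 0.5 and 32% at 0.8. In the simulation with 813 per arm, at least one of the four factors was discordant in 84% of runs at OR 1.1 and 93% at OR 1.2, falling to 3% at OR 1.5. The Protocol does not describe that procedure. It gates on association with the RE-AIM score, does not mention fits by arm, and says the reading uses effect sizes. The fault is that the comparison is left undefined, so this route is open but not prescribed.

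A reader might also infer that dropping factors must confound the retained paths. The first-step model includes the availability and affordability factors, and the section does not say that models are refitted after selection. Loss from the diagram is certain; bias in the retained coefficients from this source is not.

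The candidate count is open to challenge. Three of the four items have ordered categories, and availability may not mean the accessibility items. The range in Step 1 covers this.

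Finally, Hypothesis 3a does pose transport time or cost as a moderator of IPT relative to fluoxetine, which amounts to an interaction. It concerns remission only, and the Data analysis plan gives no method for it, so it does not fill the gap.

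**Conclusion.** The point holds as a flaw in a secondary analysis. The significance gate is explicit, and the IPT-versus-fluoxetine comparison has no stated estimand or test. Exaggeration is material for weak effects, roughly OR 1.05 to 1.15 per SD in a pooled single-factor model, and negligible from about OR 1.2 to 1.3 upwards. The 18.5% chance of admitting a null factor assumes four independent tests at 0.05 in a pooled model. The 34% figure applies only if the arms are screened separately, which the documents do not say. They support saying that arm differences can be chance, not that the plan will report false ones.

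**What to change.** In the Protocol section, with a matching paragraph in the SAP:

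- Replace the significance gate with a path diagram drawn before the data are analysed, showing treatment completion as the mediator the section already names.
- List the candidate factors by their Table 1 names, and correct the references to Table 2 and Hypothesis 1c.
- For each participant-level RE-AIM outcome, fit one model to both arms with treatment, all the pre-specified accessibility and affordability factors, and factor-by-treatment interactions.
- Report every coefficient and interaction with its 95% CI, whether or not it is significant.
- Base any statement about IPT versus fluoxetine on the interaction, with a stated alpha and multiplicity rule. The rule should say whether it spans outcomes.
- Label the analysis exploratory.

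No new data are needed; the cost is wording and some analysis time. Fewer pathways will look positive, and the interaction intervals will be wide. Under the Step 3 assumptions the per-arm SE at 813 is 0.0701, so the interaction SE is √2 × 0.0701 = 0.099, twice the pooled 0.0496. The 95% interval for a ratio of odds ratios then spans a factor of exp(1.96 × 0.099) = 1.21 either way.

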Study visits: To characterize the trajectory of symptom change during treatment, participants will be re-evaluated at the mid-point of treatment (month 1.5 for IPT and month 3 for fluoxetine). Treatment mid-point data is valuable because it can inform the minimum duration of treatment necessary to optimize mental health gains in a setting of scarce mental health resources. For example, if 90% of all observed treatment gains are achieved in the first half of treatment, subsequent implementation efforts might consider shortened courses of treatment. Participants will be assessed at month 3 (end of IPT treatment, mid-point of fluoxetine treatment) and at month 6 (end of fluoxetine treatment). For those participants who are in remission from depression and/or PTSD, follow up assessments will then continue at 9 month, 12 month and then at six month intervals until month 30 to assess for maintenance of gains and relapse. Assessments may be done at the health facility or by telephone. We are defining remission as absence of disease as defined by threshold criteria for Diagnostic and Statistical Manual of Mental Disorders-V (DSM-V) for PTSD and MDD. Those participants who have not yet remitted will be re-randomized to: switch of treatment (from IPT to fluoxetine or vice versa) or combination treatment (addition of IPT to fluoxetine or vice versa). See Figure 3.

Assessment schedule and rationale:

In order to characterize the trajectory of symptom change during treatment, participants will be re-evaluated at the mid-point of treatment (month 1.5 for IPT and month 3 for fluoxetine). Treatment mid-point data is valuable because it can inform the minimum duration of treatment necessary to optimize mental health gains in a setting of scarce mental health resources. For example, if 90% of all observed treatment gains are achieved by month 1.5, subsequent implementation efforts might consider shortened courses of treatment. Participants will be assessed at end of treatment (month 3 for IPT and month 6 for fluoxetine) and fluoxetine recipients will be tapered off the medication. At six months, participants will be re-assessed and then monitored at 6-month intervals until month 30 (Figure 3). Assessment visits may be done at the health facility or over the telephone.

Measures (Table 1): *Demographics.* We will obtain usual demographic measures, education, including individual income, assets, education and school fees, healthcare utilization, and time allocation.

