2b	MDD and/or PTSD remission at month 1.5 (treatment mid-point) for IPT and at 3 months (treatment mid-point) for fluoxetine to identify the proportion of treatment gain achieved at mid-point compared with end of treatment (month 3). Treatment Effectiveness is a key aspect of RE-AIM.
3	Maintenance of month-3 remissions from IPT or and month 6 remissions from fluoxetine at follow-up assessments (months 6 (for IPT), 9, 12, 18, 24 and 30). Maintenance of gains is an individual level measure of Maintenance in RE-AIM.
Implementation Outcomes	
4	Both IPT and fluoxetine will be acceptable treatments for delivery in primary care as determined by qualitative interviews.
5	Both IPT and fluoxetine will be appropriate treatments for delivery in primary care as determined by qualitative interviews.

- 6 Both IPT and fluoxetine will be feasible treatments as determined by completion rates. *With the exception of those who leave the study because their symptoms remit, completion rate will be used as an individual level measure of Adoption in RE-AIM.*
- 7 Both IPT and fluoxetine will have strong treatment fidelity as determined by protocol adherence to IPT and fluoxetine administration. *Fidelity is a key component of Implementation in RE-AIM.*

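### Table 2 row 2b prints month 3 as the only end-of-treatment comparator, which is also fluoxetine's mid-point; rows 2a and 3 and the visit schedule say month 6

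*Protocol*

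**What the plan says.** Table 2 of the Protocol lists the outcomes that feed the RE-AIM calculation. Row 2b concerns how much of the treatment gain has been reached half-way. For IPT it takes "MDD and/or PTSD remission at month 1.5 (treatment mid-point) for IPT". For fluoxetine it takes remission "at 3 months (treatment mid-point) for fluoxetine to identify the proportion of treatment gain achieved at mid-point compared with end of treatment (month 3"). Only one comparator month is printed for the two arms.

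The neighbouring rows distinguish the arms. Row 2a, directly above, is "MDD and/or PTSD remission from IPT or fluoxetine at month 3 (IPT) and month 6 (fluoxetine"). Row 3, directly below, is "Maintenance of month-3 remissions from IPT or and month 6 remissions from fluoxetine at follow-up assessments".

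The visit schedule agrees with rows 2a and 3. Under Study visits: "Participants will be assessed at month 3 (end of IPT treatment, mid-point of fluoxetine treatment) and at month 6 (end of fluoxetine treatment"). Under Assessment schedule and rationale: "Participants will be assessed at end of treatment (month 3 for IPT and month 6 for fluoxetine").

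Those two sections also explain why mid-point data are collected, each with an example. Study visits has: "For example, if 90% of all observed treatment gains are achieved in the first half of treatment, subsequent implementation efforts might consider shortened courses". Assessment schedule and rationale has: "if 90% of all observed treatment gains are achieved by month 1.5, subsequent implementation efforts might consider shortened courses of treatment".

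Two other places bear on the label. The Data analysis plan, under Hypothesis 1a, describes the month-3 data as end of treatment without saying for which arm. The SAP refers to the end of first-line treatment without giving a month, and it contains no mid-point analysis.

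**The concern.** A ratio of mid-point gain to end-of-treatment gain is informative only if the two visits differ. As printed, row 2b gives fluoxetine the same visit in numerator and denominator. An analyst who programmed the row as written would report 100% for fluoxetine beside a genuine estimate for IPT, and the two figures would not measure the same thing.

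The stated purpose of the mid-point data is to inform how much treatment is needed where resources are scarce, so an uninformative 100% could be taken as a finding. It might also pass unnoticed. The Protocol's account of the team's fluoxetine work in Uganda says that most of the gain came in weeks 6 to 12, with little added later, so 100% at month 3 would look like confirmation.

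**Working it through.** No sample size, power or error rate is involved, and the documents print no value of this share to reproduce. The check is to set the timings side by side and then evaluate the ratio.

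**Timings by location**

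| Place in the Protocol | IPT end of treatment | Fluoxetine mid-point | Fluoxetine end of treatment |
|---|---|---|---|
| Table 2, row 2b | month 3 | month 3 | month 3 (only month printed) |
| Table 2, row 2a | month 3 | not stated | month 6 |
| Table 2, row 3 (maintenance anchor) | month 3 | not stated | month 6 |
| Study visits | month 3 | month 3 | month 6 |
| Assessment schedule and rationale | month 3 | month 3 | month 6 |
| Data analysis plan, Hypothesis 1a | month 3 (no arm named) | not stated | month 3 (no arm named) |

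**Formula.** Share of gain at mid-point = gain(mid-point) / gain(end of treatment). Gain is taken as the proportion in remission, assuming none are in remission at entry.

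**Row 2b as printed**
- IPT: gain(month 1.5) / gain(month 3). The visits differ and the ratio is free to vary.
- Fluoxetine: gain(month 3) / gain(month 3) = 1 for any non-zero gain. For month-3 remission of 0.10, 0.20, 0.30, 0.40, 0.50 and 0.60 the result is 1.00 each time. At zero gain the ratio is 0/0 and undefined.

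**With month 6 as the fluoxetine comparator.** The share is r3/r6, where r3 and r6 are remission at months 3 and 6. The documents give no month-3 fluoxetine remission rate, so all values here are assumed.
- r3 = 0.35, r6 = 0.50: 0.35/0.50 = 0.70, against 1.00 as printed.
- r6 = 0.38, 0.50 or 0.66, with r3 from 50% to 110% of r6: the share runs from 0.50 to 1.10. It exceeds 1 when remissions are lost between months 3 and 6. The printed form returns 1.00 throughout.

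**The two examples.** Month 1.5 is 1.5/3 = 50% of the IPT course but 1.5/6 = 25% of a six-month fluoxetine course. The first-half wording and the month-1.5 wording therefore agree for IPT only.

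**The case against.** The strongest reply is that this is a slip in a label and that the surrounding text resolves it. The same sentence calls month 3 the fluoxetine mid-point and asks for a comparison with end of treatment. Rows 2a and 3 and both schedule sections give month 6, and month-6 assessments are planned. On this view the bracketed month fits IPT and the fluoxetine month was simply left out. Much of this stands: a careful analyst would probably use month 6, so the analysis is not bound to return 100%. It is not a complete answer, because the Hypothesis 1a text also attaches the end-of-treatment label to month 3 without an arm, and the SAP does not settle the matter.

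The second reply is that the quantity is peripheral. That also stands. Row 2b is a descriptive RE-AIM item and is not among the SAP's primary or secondary analyses. The Protocol ties the RE-AIM calculation to a Hypothesis 1c that does not appear in its list of hypotheses.

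A reader might infer that fluoxetine would always satisfy a 90% criterion for shorter courses. The documents do not support that. The 90% figure is absent from Table 2. It appears only in the two schedule sections, as an example of what later implementation efforts might consider, and no rule or test depends on it. Nor does the problem extend to IPT.

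**Conclusion.** The inconsistency is real and minor. Row 2b's single comparator month is wrong for fluoxetine when set against rows 2a and 3 and both schedule sections. Taken literally, it yields 100% for that arm whenever the month-3 gain is not zero, and so carries no information. The IPT contrast is correctly defined.

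The size of any distortion cannot be known from the documents. The 70% against 100% illustration rests on assumed remission rates, and on the row being programmed exactly as printed. If the analyst takes month 6 from the adjacent rows, there is no distortion. The point concerns outcome timing only and takes no position on treatment length.

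**What to change.** - In Table 2, row 2b, state the comparator by arm: IPT month 1.5 against month 3, and fluoxetine month 3 against month 6, in agreement with rows 2a and 3.
- Reconcile the two forms of the example in Study visits and in Assessment schedule and rationale, so that they refer to the same point in each arm's course.
- Reconcile the end-of-treatment label under Hypothesis 1a in the Data analysis plan with the arm-specific timing given elsewhere.

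The cost is a few wording corrections. Months 1.5, 3 and 6 are already in the assessment schedule, so no new visits or data are needed.
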